### 9.3.2.2 Secondary outcomes

The secondary outcomes are:

- Appropriateness of NOAC prescription based on national recommendations (positioning therapeutic report) ([11](#)) is planned. The reasons for NOAC initiation will be described using the following checklist. The time frame is the duration of the study visit, at the time of patient enrolment. Answers to this checklist will be validated with baseline variables already collected from medical records:
  - Patients with known hypersensitivity or with specific contraindications to the use of acenocoumarol or warfarin.
  - Patients with a history of intracranial hemorrhage (ICH) (except during the acute phase)
  - Patients with ischemic stroke who present high-risk clinical and neuroimaging criteria for ICH.
  - Patients on VKA treatment who suffer from severe arterial thromboembolic events despite good INR control.
  - Patients who have started treatment with VKA in which it is not possible to maintain INR control within range (2-3) despite good therapeutic compliance.
  - Impossibility of access to conventional INR control.
  - Other
  - Unknown
- NOAC treatment management. The following variables will be collected at time of patient enrolment:
  - history of thromboembolic and bleeding events,
  - frequency of visits to the physician,
  - first NOAC (start - end date, dose),
  - dose change/adjustment (start date - end date, new dose, reason for change)
  - new NOAC initiation (start - end date, new treatment, new dose, reason for change)Prior VKA use and reasons for switch (already collected as a baseline variable) will be also considered for this outcome. The time frame is the duration of the NOAC treatment, since first NOAC treatment initiation until the study visit date.

- Patient's knowledge about his condition. Answers (yes/no) to the questions below will be described for the whole study population, independent of NOAC type. "Yes" and "No" patient's answers must be validated by the physician (the physician will ensure that the answer is accurate by asking "Why" "Which" "What" additional questions to validate the answer). The time frame is the duration of the interview with the patient during the study visit, at the time of patient enrolment.
  - a) Do you know why you are being treated with an anticoagulant? Yes/No.
  - b) Do you know which the effect of the anticoagulant treatment is? Yes/No.
  - c) Do you know what could happen if you don't take the anticoagulant treatment? Yes/No.

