**Table 9.3.2.2:1 Treatment management variables at time of enrolment**

Variables	Obtained from patient medical records	Obtained at the study visit by direct interview with the patient
In case of previous treatment with VKA: treatment duration (start and stop date if available) and reasons for VKA treatment switch	X *	
First NOAC initiated (active substance, dose, start date, end date)	X *	
History of thromboembolic and bleeding events	X	X (if applicable)
History of NOAC treatments prior to current NOAC (if applies):  - Dose changes: start date – end date, new dose, and reason  - NOAC switch: start date – end date, dose and/or dose changes and reason	X	X (if applicable)
Frequency of visits to the physician: "How many times a year do you visit the cardiologist?"		X

\* Already obtained for primary objective.

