4.7. STUDY POPULATION

To be eligible to participate in the study, patients must meet the following selection criteria.

The patient will be considered included when he/she agrees to participate in the study by signing the informed consent.

Patients, in the hospital setting, will be included in the study if all of the following criteria are met:

1. The patient is willing and provides written informed consent to participate in this study
2. The patient is at least 18 years of age
3. The patient has a diagnosis of non-valvular atrial fibrillation
4. The patient is on treatment with NOAC according to its approved local SmPC and has initiated his first NOAC starting from November 2016

Patients will be excluded from participating in this study if they currently participate in any clinical trial of a drug or device.

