5. GENERAL STATISTICAL METHODOLOGY

The content of the clinical database shall be transferred to SAS® data files for the statistical analysis. All the statistical analyses will be conducted using the statistical program SAS®v9.3 (SAS Institute Inc., Cary, NC, USA).

Description analyses of all the variables collected should be carried out. Depending on the type of variable, the following shall be presented:

- The categorical variables shall be summarized through frequencies and percentages.
- The continuous variables shall be summarized through measures of central tendency and dispersion: mean, standard deviation, median, interquartile range and extreme values (minimum and maximum).

The variables included in the study objectives will be summarized overall and by factors of interest.

The analysis population will consist of all eligible patients (i.e. all patients fulfilling all inclusion criteria and no exclusion criteria).

If patients have missing values for an outcome, those patients will be excluded for that outcome's analysis. No type of imputation shall be made to the data and the data will be considered as missing.

The primary outcome is the usage of NOACs, in patients with NVAF, in the hospital setting, based on the baseline characteristics at the time of first NOAC initiation. Baseline (at time of first NOAC initiation) variables will be analysed descriptively by NOAC type. Treatment groups will be defined according to first NOAC prescribed.

Standardized differences between Dabigatran Etexilate and each of the other NOACs separately will be estimated for these variables (baseline characteristics). The formulas are:

For means:
$$d = \frac{(\bar{x}_{DE} - \bar{x}_C)}{\sqrt{(s_{DE}^2 + s_C^2)/2}}$$

For proportions:
$$d = \frac{(\hat{p}_{DE} - \hat{p}_C)}{\sqrt{\frac{\hat{p}_{DE}(1 - \hat{p}_{DE}) + \hat{p}_C(1 - \hat{p}_C)}{2}}}$$

Where DE is dabigatran etexilate and C is the comparator

Standardized differences higher than 10% (in absolute value) are indicative of imbalance between the compared groups.

The secondary outcomes will be carried out descriptively for the total sample, regardless of the type of NOAC prescribed to the patient.

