9.2. NOAC TREATMENT MANAGEMENT

A description of the first prescribed NOAC and other NOACs (if applicable) will be made, indicating:

- ✓ Number and percentage of patients according to NOAC type and dose
- ✓ Time in treatment calculated as the difference between start date and end date, if both are available and in other case informed consent date will be used (time to beginning study); it will be described as quantitative variable.
- ✓ NOAC Dose; it will be described as qualitative variable.
- ✓ Number and percentage of patients who need discontinue treatment or dose adjustment or change a new NOAC; in this case, reason for change.
- ✓ Number and percentage of patients who change other NOAC, including type of new NOAC or new doses, time in treatment if start and end dates, and time after first NOAC.

On the other hand, frequency of visits to the physician will be assessed quantitatively and qualitatively.

A descriptive analysis of the history of thromboembolic and hemorrhagic events presented by the patients will be carried out. First, the number and percentage of patients with or without thromboembolic and hemorrhagic events would be provided. A description will be made of the type of event suffered, if it was related to NOAC and as well as the number of times, for the following two types of events:

Thromboembolic events:

- TIA
- Ischaemic stroke
- Haemorrhagic stroke
- Embolism systemic
- Deep vein thrombosis
- Pulmonary embolism
- Stable angina
- Unstable angina
- Myocardial infarction without ST segment elevation
- Myocardial infarction with ST segment elevation

Bleeding events:

- Intracranial
- Digestive
- Genitourinary
- Gingival
- Nasal
- Pulmonary
- Articular-muscular
- Conjunctival
- Other

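### SAP 9.2 gives two inconsistent rules for time in treatment, so switchers' durations depend on which bullet is programmed and on how unrecorded stop dates are handled

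*SAP*

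**What the plan says.** The list in SAP 9.2 opens with its scope: "A description of the first prescribed NOAC and other NOACs (if applicable) will be made, indicating". What follows therefore applies to first and later NOACs alike.

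- **Second bullet.** "Time in treatment calculated as the difference between start date and end date, if both are available and in other case informed consent date will" stand in. The fallback applies whenever the two dates are not both present. It does not ask why a date is absent.
- **Fifth bullet.** For patients who change NOAC it requests a description "including type of new NOAC or new doses, time in treatment if start and end dates, and time after first NOAC". No fallback is given.

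Three other places bear on this:

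- SAP 4.7, criterion 4: "The patient is on treatment with NOAC according to its approved local SmPC and has initiated his first NOAC starting from November 2016". The current NOAC is thus ongoing at the visit.
- Protocol 9.3.2.2, on treatment management: "The time frame is the duration of the NOAC treatment, since first NOAC treatment initiation until the study visit date".
- SAP 5: "No type of imputation shall be made to the data and the data will be considered as missing".

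Protocol Table 9.3.2.2:1 lists start and end dates as data items, both for the first NOAC and for switches. The Data sources entry of the protocol abstract accepts that some chart data may be missing, without giving a rate.

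**The concern.** Treatment management is a named secondary objective, and time on each NOAC is one of its outputs. Two programmers working from SAP 9.2 could produce different tables for switchers.

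The fifth bullet taken literally would summarise time on the new NOAC only from second courses that had already ended, leaving out the usual case. The second bullet taken literally would treat a first NOAC that was stopped and replaced, but whose stop date is not in the chart, as if it ran to consent. That overlaps the next drug. It also fills in a missing date, which SAP 5 rules out.

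**Working it through.** The documents state no figure for time in treatment, switch rate or missing dates, so there is nothing to reproduce. The check compares the two bullets case by case and then does date arithmetic on assumed patients.

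**1. The two bullets side by side**

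| Course | Second bullet | Fifth bullet, literal |
|---|---|---|
| First NOAC, stopped, end date recorded | end − start (correct) | not addressed |
| First NOAC, stopped, end date not recorded | consent − start (too long) | not addressed |
| Second NOAC, ongoing at visit | consent − start (time to date) | no value |
| Second NOAC, ended, both dates recorded | end − start | end − start |
| Any course, start date not recorded | consent date substituted (meaningless) | no value |

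The bullets disagree in the third row, which criterion 4 makes the normal row for a patient with one switch.

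**2. A replaced first NOAC with no recorded end date**

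Excess = (consent − start) − (true stop − start) = consent − true stop.

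Assumed dates: first NOAC 1 Jan 2017, switch 1 Jul 2017, consent 1 Feb 2018.

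- True first course: 181 days. Second course to consent: 215 days. Sum: 181 + 215 = 396 days, the elapsed time.
- Second bullet: the first course becomes 396 days, an excess of 396 − 181 = 215.
- The two courses then sum to 396 + 215 = 611 days within 396 elapsed.

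Other assumed dates within the study calendar give an excess from 45 days (switch 1 Oct 2017, consent 15 Nov 2017) to 484 days (switch 1 Feb 2017, consent 31 May 2018). If the end date is recorded, the excess is 0.

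**3. Effect on means**

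Let s be the share of switchers, m the share of their first-NOAC end dates missing, and the gap 215 days. All are assumed. N = 1000 is the planned size.

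- Patients affected = 1000 × s × m. From 1000 × 0.02 × 0.05 = 1 to 1000 × 0.10 × 0.50 = 50.
- Shift in mean first-NOAC time, all patients = s × m × 215. From about 0.2 to 10.8 days.
- Shift among switchers = m × 215. From 0.05 × 215 = 10.8 to 0.50 × 215 = 107.5 days.

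**4. The fifth bullet read literally**

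Let f be the share of switchers who have also left the second NOAC, a the mean time to date of ongoing second courses, and b the mean length of ended ones. The literal summary reports b. All switchers average (1 − f)a + fb. The shortfall is (1 − f)(a − b).

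| f (assumed) | a, months | b, months | Literal summary | All switchers | Shortfall |
|---|---|---|---|---|---|
| 0.05 | 6 | 2 | 2.0 | 5.8 | 3.8 |
| 0.10 | 6 | 2 | 2.0 | 5.6 | 3.6 |
| 0.30 | 6 | 2 | 2.0 | 4.8 | 2.8 |
| 0.10 | 6 | 4 | 4.0 | 5.8 | 1.8 |

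If ended and ongoing courses had the same mean, the shortfall would be zero, but the summary would still rest on a fraction f of the switchers.

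**The case against.** A reader might infer that the plan loses every ongoing second NOAC. The documents do not support that. The opening line of the list brings later NOACs under the second bullet, which gives an ongoing second course a duration to consent. The fifth bullet is mainly a count of patients who change, and its phrase on time is elliptical. It may be shorthand for the variable already defined. What stands is that it states a condition the second bullet does not, and nothing says which governs.

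A reader might also infer that durations in switchers are simply wrong. That goes too far. The first-NOAC error needs an unrecorded stop date, and that date is a planned item. For treatments before the current NOAC, Protocol Table 9.3.2.2:1 lets the interview supplement the chart. Protocol 9.6 and 9.8 also describe eCRF checks for missing or illogical entries. These safeguards lower the likely count. They do not change what the derivation does when a date remains missing, and Protocol 9.8 plans no routine source data verification.

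Nor does the consent-date fallback as a whole contradict SAP 5. An ongoing course has no end date to be missing. Closing it at consent is censoring, and it agrees with the time frame in Protocol 9.3.2.2. The conflict arises only where the fallback fills in a date that exists but was not recorded.

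**Conclusion.** The inconsistency is real and worth correcting. For an ongoing second NOAC the two bullets give different answers: a time to date under one, no value under the other read literally. For a stopped first NOAC with no recorded end date, the second bullet can credit time that belongs to the next drug, and in that case it conflicts with SAP 5.

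The size cannot be fixed from the documents. Under the assumed ranges, the effect on mean first-NOAC time is small overall (0.2 to 10.8 days) and larger among switchers (10.8 to 107.5 days with a 215-day gap). The contrast for second courses depends on the literal reading of the fifth bullet and on ended courses being shorter than ongoing ones.

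The reach is limited to one derived descriptive variable in a secondary outcome. The primary outcome, the standardized differences, the sample size, and the counts, types and reasons for switching are unaffected.

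**What to change.** State one rule in SAP 9.2 for every course, first or later:

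1. Close a course at the consent date only if it is recorded as ongoing at the visit, and label the result as time to date.
2. For a stopped course with no recorded end date, leave the duration missing under SAP 5 and report how many there are. As an option, add a flagged sensitivity summary that takes the next course's start as the end. It assumes no gap between courses and is itself an imputation, so it should not be the main result.
3. Do not substitute the consent date for a missing start date.
4. Remove the both-dates condition from the fifth bullet, so that ongoing second courses are included under rule 1.

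The start and end dates needed are already planned items; the ongoing status should be confirmed as an eCRF field or derived from the current NOAC. The cost is a few durations becoming missing, plus minor changes to SAP wording and derivation code.

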
systemic embolism prevention in patients with NVAF)
 

- To evaluate the reason of NOAC initiation.

 
Variables collected at time of study visit / enrolment (new data):
 

- In order to answer the secondary objective regarding patient's knowledge, all patients at study visit will be asked some questions by the physician.

- In order to answer the secondary objective regarding treatment management, the following variables will be collected:

- History of NOAC treatments prior to current NOAC (if applies):

- Dose changes: start date – end date, new dose, reason

- NOAC switch: start date – end date, dose and/or dose changes and reason

- Frequency of visits to the physician

- History of thromboembolic and bleeding events at time of enrolment

 
Even though this NIS is based on already existing (retrospective) data and also new data obtained at the visit date, AE management and AE reporting becomes relevant as data extraction from patient's individual medical records will be performed (study data collection) and reviewed. AE management and reporting has to be implemented and followed as outlined in section 11.
			
Data sources:	
Patient data will be collected from patient medical charts and will be entered to an eCRF by the Investigator. Most of data will be available in the charts but as a routine clinical practice, some data could be missing.
 
Data regarding the ad hoc questionnaire will be obtained from an interview between the physician and the patient according to instructions. Investigator will enter these data into the eCRF system.
		
Study size:	
It is planned that a total of approximately 1000 patients will be recruited for the study. Additional details regarding sample size considerations are provided in Section 9.5.
		
Data analysis:	
A Data Management Plan (DMP) and Statistical and Epidemiological Analysis Plan (SEAP), will be prepared to describe all processes, treatment and specifications for data collection, cleaning, validation
		

Name of company: Boehringer Ingelheim			
Name of finished medicinal product: Pradaxa®			
Name of active ingredient: B01AE07 - Dabigatran etexilate			

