9. SECONDARY OBJECTIVES

9.1. APPROPRIATENESS OF NOACs PRESCRIPTION

First of all, appropriateness of NOAC prescription based on national recommendations (positioning therapeutic report) is planned, for the entire eligible patients. For this, it will be reviewed if the presence of at least one of the below clinical situations or situations related to INR control were met.

- Patients with known hypersensitivity or with specific contraindications to the use of acenocoumarol or warfarin.
- Patients with a history of intracranial hemorrhage (ICH) (except during the acute phase).
- Patients with ischemic stroke who present high-risk clinical and neuroimaging criteria for ICH.
- Patients on VKA treatment who suffer from severe arterial thromboembolic events despite good INR control.
- Patients who have started treatment with VKA in which it is not possible to maintain INR control within range (2-3) despite good therapeutic compliance.
- Impossibility of access to conventional INR control.
- Other reason
- Unknown

The reasons for initiation of the first NOAC will be described in first place, broken down between clinical reasons or situations related to INR control. In case of other reason, it should be specified.

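### SAP 9.2 classes haemorrhagic stroke as a thromboembolic event and does not link it to intracranial bleeding

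*SAP*

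**What the plan says.** SAP 9.2 covers the history of events as part of treatment management. The opening summary is at patient level: "First, the number and percentage of patients with or without thromboembolic and hemorrhagic events would be provided". The text then asks for the type of event, "if it was related to NOAC and as well as the number of times", under two headed lists.

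- The thromboembolic list has ten items. "Haemorrhagic stroke" is the third, after TIA and ischaemic stroke.
- The bleeding list has nine items. *Intracranial* is the first, with no definition, exclusion or cross-reference.

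The protocol names the outcome but not its components. The wording in Table 9.3.2.2:1 is "History of thromboembolic and bleeding events", and sections 9.3.2.2 and 9.7.1 add no list. SAP section 5 sets the scope of the reporting: "The secondary outcomes will be carried out descriptively for the total sample, regardless of the type of NOAC prescribed to the patient".

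**The concern.** Bleeding and thromboembolism are the two opposing outcomes of anticoagulant treatment. A haemorrhagic stroke is a bleed, and the plan as written puts it on the thromboembolic side. The class percentages are the first result that SAP 9.2 asks for and the ones most likely to be quoted. A patient in the wrong class can raise the thromboembolic figure, lower the bleeding figure, or both. With no stated rule on the intracranial item, the bleeding figure also depends on whether a site enters the same bleed a second time. The study plans at least 102 sites.

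**Working it through.** No figure in the plan belongs to this point, so there is none to reproduce. The check compares the passages, works through the possible entry patterns, and scales one patient.

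**1. Does the SAP's own language support the placement?** It does not. SAP 9.2 itself calls the second class haemorrhagic. The footnote to the HAS-BLED table in SAP 8.3 gives intracranial haemorrhage as an example of a haemorrhagic process. The disease lists in protocol Table 9.3.3:1 and SAP 7.3 pair TIA with ischaemic stroke only, and keep bleeding as a separate entry.

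**2. Is there a mapping elsewhere?** None was found. MedDRA coding in SAP 5 and 11.1 applies to adverse drug reactions and fatal adverse events, and in SAP 7.3 to write-in diseases. None of these reaches the lists in 9.2. In the ENCePP checklist (protocol Annex 2), the item on a coding system for outcomes is ticked No.

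**3. What happens to each entry pattern?** The table takes the lists literally and reports the two classes separately. Correct means that the class count matches what it would be with haemorrhagic stroke treated as a bleed.

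| Items entered for the patient | Thromboembolic count | Bleeding count |
|---|---|---|
| Haemorrhagic stroke only | counted, wrong | not counted, wrong |
| Haemorrhagic stroke and intracranial | counted, wrong | counted, correct |
| Haemorrhagic stroke and gingival bleed | counted, wrong | counted, correct |
| Haemorrhagic stroke and ischaemic stroke | counted, correct | not counted, wrong |
| Haemorrhagic stroke, ischaemic stroke and intracranial | counted, correct | counted, correct |

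The two errors therefore come from different groups of patients. The thromboembolic percentage is too high by the patients with no other thromboembolic item. The bleeding percentage is too low by the patients with no bleeding item. One count cannot serve for both.

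**4. How much does one patient matter?** The planned size is about 1000 (protocol 9.5). The shift per misplaced patient is 100/N = 100/1000 = 0.1 percentage point in each percentage affected. The documents give no frequency of haemorrhagic stroke and no split across the patterns above, so no total follows.

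**5. Event counts.** If one bleed is entered under both items, it appears once in each list when the number of times is tabulated.

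**The case against.** **The item rows already show it.** Haemorrhagic stroke will have its own row, so a reader can see the grouping. That stands in part. Patients can have several events, however, so the rows alone do not give the corrected patient-level percentages.

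**A rule may exist elsewhere.** The eCRF is not available, and the data management plan is a separate document. Either could tell sites how to enter such an event. This stands as a limit on certainty, but the SAP defines the tabulation and states no rule.

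**The summary may be one combined figure.** A single percentage of patients with any event of either kind would not change. The wording does not exclude this, but the two separate lists make separate percentages likelier.

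**The thromboembolic list is loose anyway.** It also contains stable angina. This is a fair objection: moving one item removes a bleed from the class but does not make it a strict thromboembolic class.

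**A reader might infer that such patients are bound to be present**, because a history of intracranial haemorrhage is one of the listed reasons for starting a NOAC in SAP 9.1. The documents do not support this. A checklist option carries no frequency. Under the time frame that protocol 9.3.2.2 gives for treatment management, "The time frame is the duration of the NOAC treatment, since first NOAC treatment initiation until the study visit date", a haemorrhage that led to the first NOAC would fall before the window.

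**Conclusion.** The point holds as a minor classification error. Following SAP 9.2 as written puts a bleed in the thromboembolic percentage, and can leave it out of the bleeding percentage. The size is 0.1 point per affected patient at N = 1000, in whichever percentage that patient affects. The total is unknown. The conclusion assumes that the two classes are reported separately and that no unseen recording rule already resolves the overlap.

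A reader might go further and infer that both percentages must be wrong, or that the comparison of dabigatran with other NOACs is distorted. The documents support neither. The bleeding percentage is right for any patient who also has a bleeding item, and the thromboembolic percentage is right for any patient with another thromboembolic item. Secondary outcomes are described for the total sample and not by NOAC. The primary variables are age, CHA₂DS₂-VASc and HAS-BLED at first NOAC start. The protocol takes them from medical records, and nothing says that they are derived from the 9.2 lists.

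**What to change.** In SAP 9.2, add a derivation rule for the patient-level class percentages: haemorrhagic stroke counts as a bleeding event, within the intracranial item, with each patient counted once, and does not count as thromboembolic. Keep the item-level rows as they are collected. Under the number-of-times table, add a footnote that one bleed may have been entered under both items.

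The cost is a change to the table programming and a line or two of SAP text, made before the tables are produced. It needs no new data, because SAP 9.2 already describes events by type.
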